EN-CAMHS 1 stakeholders recommended we implement a digital solution to address the current problems of poor communication, missing information, poor data quality and lack of guidance for families about what to expect of the referral journey. The design and development of the digital tool will specifically address the accessibility needs of referrers. We intend to explore issues of digital accessibility in the consultations (WP1) and in the co-design workshops with participants. We shall also consider the three key elements of digital exclusion: lack of digital access; lack of digital skills; lack of confidence to use digital. We will explore these challenges in the co-design workshops, with stakeholders in consultation and with our advisory groups. The digital tool will supplement rather than supplant traditional modes of referral; traditional (e.g. paper based) modes of referral will remain. However, we anticipate that our digital tool will enable more people to make more successful referrals than before.

We shall also **generate new knowledge** about the patterns of referrals into CAMHS, by automating data collection through the digital tools and thereby enabling services and NHS England to understand referral and treatment data in greater detail than ever before. We see **enormous potential** in this project and its learnings/outputs for cross-pollination to **other services experiencing similar problems**.

1. Referrals overwhelming CAMHS

- We **cannot** increase CAMHS staff levels or change what it can provide.
- We **can** make the referral process work better and with greater satisfaction for referrers and for those being referred.
- We **can** increase confidence in CAMHS alternatives and increase follow-through into CAMHS alternatives.
- We **can** help CAMHS prioritise the needs of those it is designed to help.

2. Quality of referrals is poor

- We **can** provide clear, accessible guidelines to make appropriate referrals.
- We **can** validate input on the referral form and ensure all required information is completed pre-submission.
- We **can** raise awareness about what a good referral is.
- We **can** educate people about common referral mistakes.

3. Poor experience of referral

- We **can** explain the referral process clearly.
- We **can** outline key steps in the referral journey and inform people about the expected waiting times for the local CAMHS triage process.

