We shall use the NASSS-CAT toolkit [32] to guide the implementation and evaluation of the digital tool across CAMHS sites. This entails running a NASSS-CAT workshop with key stakeholders from each CAMHS service in order to introduce and complete the assessment as well as create a risk management and mitigation plan. The workshop will identify gaps in information that will need to be identified and incorporated. Once this is done, the risk plan will be regularly reviewed throughout the implementation process. Insights from this will be turned into an implementation toolkit that sets out a standardised evidence-based approach along with common risks and how they can be managed or mitigated. We shall also use the NASSS-CAT implementation toolkit to explore the potential, enablers and barriers of embedding a new CAMHS referral mechanism across different types of referrers and across CAMHS with various configurations. The NASSS-CAT toolkit will be used to guide implementation discussions with key stakeholders. Specifically, we will use the NASSS framework to address key considerations for the implementation digital transformation covering the key NASSS areas: the illness/condition in question; the technology; the value proposition; the intended adopters; the organisation; external context for innovation. The questions from the NASSS-CAT toolkit on these areas will be tailored for the EN-CAMHS project and used to structure the topic guides for interviewers with referrers.

We shall collect referral data from each referrer and from the CAMHS site referred into. We shall collect number of referrals made via the digital tools and numbers made by traditional referral mechanisms. We shall collect usage and engagement data with the tool, including numbers of referrals completed to an endpoint (either referral sent to CAMHS or to alternative help). We shall collect data on accepted/rejected referrals made by participant referrers to CAMHS using a) the tool and b) traditional modes of referral. Co-design workshops with each CAMHS provider will help us understand which data can be captured, and how each provider records the data.

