method and we will explore whether this differs between type of referrer. We shall explore 'effective engagement' with the tool: the ability of referrers to complete a successful referral with the tool. A successful referral can mean either a referral to CAMHS or to an alternative source of support for the CYP. We shall analyse the rate of successful referrals made using the tools against those made using traditional referral processes.

Qualitative data analysis: We will conduct qualitative interviews (n=25) with referrers who have used the digital tool to highlight any potential barriers to implementation. Additionally, WP3 Qualitative data analysis: Anonymised transcripts will be analysed using NATCEN Framework Analysis methodology set out by Ritchie and Spencer [43], outlined in Ritchie et al. [44], and using Nvivo 12, as this has a Framework Matrices Tool [45], allowing for both inductive and deductive coding. Coders will meet regularly to discuss codes and develop a provisional framework. During constant comparison of new data, this provisional framework will be amended to accommodate new codes and remove old codes that become superfluous. The final coding framework will be presented to the study advisory group to ensure interpretations of data remain grounded in the experience of mental health services. Analysis will occur in parallel to data collection. The whole team will agree when data saturation has occurred.

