8.2 Outputs

Key indicators of success will be defined by the following criteria:

- Digital referral platform successfully tested across minimum 5 CAMHS.
- Stakeholders successfully recruited to roundtable events and prioritisation of features consultation.
- CAMHS referral technical standards defined.
- Co-design of digital tool completed with outputs produced and published.
- Quantitative referral data collected and analysed from CAMHS sites. A reduction in the proportion of unsuccessful referrals is achieved when made through the ENCAMS platform compared to the usual referral processes.
- Following AMUsEd framework, engagement and usage metrics with the digital platform demonstrate that the platform is usable and acceptable to referrers.
- Qualitative intervention data successfully collected and analysed. Qualitative interviews demonstrate usability and acceptability of the platform to referrers and key stakeholders, including GPs, school staff, health and educational professionals and CYP and families/carers themselves. Qualitative interviews demonstrate a preference for the platform by referrers and key stakeholders, including GPs, school staff, health and educational professionals and CYP and families/carers themselves.
- Evaluation successfully completed.
- Sustainability plan developed that secures future plan for the CAMHS digital tool supported for use within the NHS.

Specific outputs for WP1

- Report detailing the changing CAMHS landscape (from roundtables) and how the digital tool aligns with newly configured CAMH services.
- Clear set of priorities and requirements for the revised CAMHS referral process, ranked by Must Have, Should Have, Could Have and Won't Have (MoSCoW) to enable the technical build in Work Package 2.
- A set of technical referral standards for the digital tool for development in WP2.

Finally, we aim to produce 4 peer-reviewed academic publications during the project.

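### The success-rate comparison counts only referrals made by each route, with no rule for tool entries that are not submitted or are later sent traditionally

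*Protocol*

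**What the plan says.** Section 4.1 (WP3) fixes the data for the comparison. Volumes: "We shall collect number of referrals made via the digital tools and numbers made by traditional referral mechanisms". Outcomes: "We shall collect data on accepted/rejected referrals made by participant referrers to CAMHS using a) the tool and b) traditional modes of referral". Section 4.2 fixes the analysis: "We shall analyse the rate of successful referrals made using the tools against those made using traditional referral processes". Section 8.2 makes the result an indicator of success: "A reduction in the proportion of unsuccessful referrals is achieved when made through the ENCAMS platform compared to the usual referral processes". All four are framed on referrals made.

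Section 2 describes what the tool is meant to do before a referral exists. Point 2 says it can validate the form and "ensure all required information is completed pre-submission"; point 4 adds automated checking of documents before submission. The same section says that traditional modes, such as paper, will continue alongside the tool.

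Two further planned measures concern the tool alone. Section 4.1 collects usage data, "including numbers of referrals completed to an endpoint (either referral sent to CAMHS or to alternative help"), and section 4.2 explores effective engagement, meaning "the ability of referrers to complete a successful referral with the tool". Section 4.2 also defines success broadly: "A successful referral can mean either a referral to CAMHS or to an alternative source of support for the CYP".

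**The concern.** The denominator on the tool side is partly produced by the tool. An incomplete case sent on paper becomes a referral, can be rejected, and counts against the traditional route. The same case stopped or abandoned in the tool never becomes a tool referral. If the referrer then uses the traditional route, any rejection is counted there.

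Section 1 (point 7) says CAMHS now triages documentation that is often incomplete or inaccurate, so it is plausible that unsubmitted entries are weaker than average. In that case the statistic named in 8.2 can improve although no child's outcome has changed. It would also hide abandonment, which is where the digital exclusion raised in research question 3 could show itself.

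**Working it through.** The Protocol gives no figure to reproduce: section 6.3.1 declines a power calculation, and no abandonment or re-sending rate is stated. The check is a deterministic count with **no true tool effect**.

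**Inputs**
- Unsuccessful proportion on either route: 25%, rounded from section 1 (point 2), which reports almost a quarter.
- Started referrals: 200 on each route (assumption; equal volumes).
- *b*: share of tool entries not submitted (assumption).
- *q*: share of those that would have been unsuccessful (assumption).
- *r*: share of those re-sent traditionally (assumption).

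**Formulas, on referrals made**
- Tool unsuccessful = (0.25 − bq) / (1 − b)
- Traditional unsuccessful = (0.25 + bqr) / (1 + br)

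**Worked case, b = 10%, q = 50%**
- Tool: (0.25 − 0.05) / 0.90 = 22.2%.
- Traditional, none re-sent: 25.0%. Apparent reduction 2.8 points.
- Traditional, all re-sent: (0.25 + 0.05) / 1.10 = 27.3%. Apparent reduction 5.1 points.

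**Other values** (negative gap = tool looks better)

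| b | q | Tool | Traditional, none re-sent (gap) | Traditional, all re-sent (gap) |
|---|---|---|---|---|
| 5% | 50% | 23.7% | 25.0% (−1.3) | 26.2% (−2.5) |
| 10% | 25% | 25.0% | 25.0% (0) | 25.0% (0) |
| 10% | 75% | 19.4% | 25.0% (−5.6) | 29.5% (−10.1) |
| 20% | 50% | 18.75% | 25.0% (−6.25) | 29.2% (−10.4) |
| 20% | 75% | 12.5% | 25.0% (−12.5) | 33.3% (−20.8) |
| 20% | 10% | 28.75% | 25.0% (+3.75) | 22.5% (+6.25) |

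The second row shows that average unsubmitted entries cause no bias. The last row shows the sign reversing when they are better than average: (0.25 − 0.02) / 0.80 = 28.75% against (0.25 + 0.02) / 1.20 = 22.5%.

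**Counting by route first attempted.** If every case keeps the outcome it would have had and stays where it was started, both routes return 50/200 = 25.0% and the gap is zero.

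**Why success per entry started cannot replace this.** In the worked case 20 of 200 tool entries are not submitted, and 40 of the 180 submitted are unsuccessful. Per entry submitted the tool shows 40/180 = 22.2%. Per entry started, with every unsubmitted entry counted as a failure, it shows (40 + 20)/200 = 30.0%. The true 25.0% lies between. Setting 30.0% against a traditional rate per referral sent would penalise the tool, because abandoned paper forms are not seen.

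**Diverted entries.** Under 4.2 an entry directed to alternative support is a success, so it stays in the tool's count. If the 10% in the worked case were diverted rather than abandoned, the tool would show 0.25 − 0.05 = 20.0% unsuccessful. That follows from the definition of success and is separate from entries dropping out. Such entries are absent only from the accepted/rejected data of 4.1, so the two sections need to be read together when the indicator is computed.

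**The case against.** Several points on the other side stand.

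- A reader might infer that the plan measures success only on submitted referrals. It does not: completion to an endpoint and effective engagement are planned, so abandonment may be visible. But both are tool-only and neither is tied to the comparison or to 8.2.
- A reader might infer that stopped entries will reappear under the traditional route. The Protocol says only that the route stays open; re-sending is an inference. The bias can arise without it and grows with it.
- A reader might infer that the basis favours the tool by construction. It does so only if unsubmitted entries are worse than average. Section 1 (point 2) attributes unsuccessful referrals to inappropriateness or threshold rather than missing fields, and abandonment through poor digital access, skills or confidence need not track eligibility.
- The section 2 list describes intentions for a tool still to be co-designed. Nothing in it says that a complete but weak referral would be blocked, and a form completed and accepted because of a prompt is a real benefit, not an artefact.

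It can also be said that this is a feasibility study with no primary outcome and no hypothesis testing (sections 3 and 6.3.1), and that denominators belong in a statistical analysis plan, which was not available here. This answers less. Research question 6 asks for the comparison, 8.2 makes its direction a mark of success, and bias does not depend on a test. The referrals-made basis is written into the Protocol, and a later analysis plan cannot recover a link between routes that was never recorded.

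**Conclusion.** The concern holds in a limited form. The comparison and the 8.2 indicator are conditioned on referrals made, the tool's intended checks affect that condition, and no rule covers unsubmitted or re-sent entries. With 25% unsuccessful, 5–20% of tool entries unsubmitted and 50–75% of those unsuccessful, the spurious reduction runs from 1.3 points (5%, 50%, none re-sent) to 20.8 points (20%, 75%, all re-sent). These shares are assumptions, as are equal starting volumes, and the direction depends on unsubmitted entries being worse than average. The documents do not support saying that the tool must look better, or by how much. They do show that the indicator, as written, could be met with no true effect.

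**What to change.** In 4.1, 4.2 and 8.2:

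1. Flag participant referrers' cases that were started in the tool and later sent traditionally. Count each once, under the route first attempted, for both the comparison and the indicator.
2. Specify that the tool analytics capture entries started. Section 5 says only that usage and engagement are collected through inbuilt analytics; it does not say that starts are logged.
3. Report the tool's started, submitted and accepted or diverted counts beside the comparison.
4. Where cases cannot be linked, show success per entry started and per entry submitted as a range. Do not judge the indicator on the per-started figure alone, because abandoned traditional forms are not observed.

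Section 4.1 leaves it to provider workshops to establish which data can be captured, so the flag should be requested there, before WP3 data collection begins. The cost is Protocol wording, one data flag and slightly more analysis. The tool's rate may come out less favourable, and some entries opened only to browse may be counted as started.

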3 RESEARCH QUESTION/AIM(S)

Our overarching aim is to improve the CAMHS referral process for CYP, their families and carers, as well as for health, education and CAMHS professionals so that CYP receive the help they need as quickly as possible.

Research questions:

1. Using the findings from EN-CAMHS 1 and stakeholder consultation, can we develop a set of national standards for digital CAMHS referral processes?
2. Can we translate the prioritised features from EN-CAMHS 1 of a digitally-led, intelligent CAMHS referral process into a usable, acceptable and widely accessible platform that is nationally standardised, locally adaptable and sustainable?
3. Can we address concerns about digital exclusion and other identified health inequalities through the newly developed CAMHS referral mechanisms?
4. How do referrers, including GPs, school staff and children/young people/families perceive the usability and acceptability of the digital tool?
5. How do referrers use and engage with the tool?
6. How do rates of successful referrals with the tool compare to traditional modes of referral?

There are no primary nor secondary outcome measures for this study as this is a feasibility study to evaluate usage and acceptability of the co-created tool using data collected from referrers. These data will be a combination of quantitative data on usage and engagement and qualitative data from semi-structured interviews with 25 referrers.

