- Ensure accessibility support (WCAG2.2 and assistive technology, translations of the tools etc) is extensive and supports needs identified by stakeholder consultation (Digital Accessibility Working Group n=10) and in collaboration with PPIE, YPAG and PPAG. This group will be formed from the project with characteristics derived from accessibility needs identified in the stakeholder codesign groups and from ENCAMS 1. This group shall meet twice during the co-design process to review the tool and suggest accessibility enhancements. Every effort will be made to incorporate suggestions made by this group into the digital tool.

National and locally relevant content (e.g. links to alternative sources of help) will be developed in collaboration with CAMHS professionals at each of the providers and in collaboration with the CAMHS professionals on our research team. We shall run a workshop at each of the chosen providers with 5-8 Trust staff members from different departments, for example, clinical IT, digital strategy, CCOs, research. These workshops will undertake a full assessment of the capability of the Trust to implement, identify risks to implementation, and create a plan to manage and mitigate them. We have costed a professional content designer to ensure the quality and accessibility of content developed. We have provisional confirmation from the following CAMHS providers for WP2 and WP3: Manchester University NHS Foundation Trust (South Manchester, North Manchester); Greater Manchester Mental Health NHS Foundation Trust (Bolton, Wigan); East London NHS Foundation Trust (South Bedfordshire and Luton).

Our team has worked across many NIHR funded digital mental health projects. We shall use the same approach in this project, developing with an iterative Agile and a user-centred design approach to co-develop the platform. This approach enables the software team to work closely with and respond to the needs of the end user. This will be delivered through (a) user research (b) moderated usability testing with end users. This design approach will follow the below stages:

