8 DISSEMINATION POLICY

8.1 Dissemination policy

The datasets arising from the study will be protected by know-how, copyright and database rights (which are automatic rights and do not need to be registered). The copyright for the foreground IP will be held by GMMH.

The draft final report will be due to the NIHR two weeks after the end of the contract. The NIHR will contact the team at least three months before this time with more specific advice. Further guidance on writing the draft final report can be found on the Information for Authors webpage. This guidance is regularly updated and will change during the lifespan of the project. We must make sure to use the most up to date guidance when drafting the report.

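### Section 8.2 counts any fall in unsuccessful referrals as success, although the only outcome collected for both routes is an accept/reject decision by involved sites, with no masking of route described

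*Protocol*

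**What the plan says.** **The question and the data.** Research question 6 (protocol section 3) asks: "How do rates of successful referrals with the tool compare to traditional modes of referral". For WP3, section 4.1 states "We shall collect referral data from each referrer and from the CAMHS site referred into" and then "We shall collect data on accepted/rejected referrals made by participant referrers to CAMHS using a) the tool and b) traditional modes of referral". It also collects counts of referrals by each route and usage data from the tool, but accepted/rejected status is the only result of a referral recorded for both routes. The protocol does not describe hiding the route from the deciding staff, independent review of decisions, or a common acceptance threshold.

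**Who is involved.** Under WP2 in section 4.1, national and local content "will be developed in collaboration with CAMHS professionals at each of the providers". The providers provisionally confirmed for both WP2 and WP3 include "Greater Manchester Mental Health NHS Foundation Trust (Bolton, Wigan"). That Trust (GMMH) is the sponsor, and section 8.1 adds: "The copyright for the foreground IP will be held by GMMH".

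**Analysis and success rule.** Section 4.2 plans to set the rate of successful referrals through the tool against the rate by traditional routes, and says "A successful referral can mean either a referral to CAMHS or to an alternative source of support for the CYP". Section 8.2 lists as a key indicator of success: "A reduction in the proportion of unsuccessful referrals is achieved when made through the ENCAMS platform compared to the usual referral processes". It attaches no margin, interval or condition on sites. Section 3 calls this a feasibility study without primary or secondary outcomes, and section 6.3.1 says that hypothesis testing is not the aim.

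**The concern.** Accepting or rejecting a referral is a judgement. Here it is made at sites that have contributed to the tool and, as far as the protocol says, can see which route a referral came by. If staff treat tool referrals more leniently, the rejection rate on that route falls even when the referrals are no better. Section 8.2 would record this as success, because it asks only for a reduction of any size.

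GMMH adds a conflict of ownership: as sponsor, copyright holder and a provisional evaluation site, it would supply decisions on its own tool. The result also matters beyond this study, because WP4 plans to lobby for national implementation.

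**Working it through.** The protocol gives no effect size, number of referrals or error rate for this comparison, so there is no figure to reproduce. The check has four steps.

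**1. What the outcome means.**
- Section 1 (point 2) uses unsuccessful for referrals that CAMHS turns down as inappropriate or below threshold.
- Section 4.1 collects accepted/rejected by route. As tool usage data, it also collects referrals completed to an endpoint, meaning sent to CAMHS or to alternative help.
- Section 4.2 counts a referral to CAMHS or to alternative support as successful.
- Section 8.2 does not define unsuccessful.

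If unsuccessful means rejected by CAMHS, site leniency changes the outcome. If success means sent to CAMHS or directed elsewhere, it does not; but section 4.1 lists that endpoint only as tool usage data, with no counterpart for the traditional route.

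**2. Size, if unsuccessful means rejected.** Inputs: usual rejection r = 25%, rounded up from the nearly one quarter in section 1; no true effect of the tool; and a share L of tool referrals accepted that would otherwise be rejected. L is an assumption, because the documents give nothing on it.

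Tool rejection = r × (1 − L); apparent reduction = r × L.
- L = 1 in 10: 0.25 × 0.90 = 22.5%, a reduction of 2.5 points.
- L = 1 in 4: 0.25 × 0.75 = 18.75%, a reduction of 6.25 points.
- With r = 20% the reductions are 0.20 × 0.10 = 2.0 and 0.20 × 0.25 = 5.0 points.

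**3. If it happens only at the two GMMH localities.** Assume that k sites contribute equally, with k from 5 to 8 as planned. Pooled reduction = r × L × 2/k.
- k = 5: 2.5 × 0.40 = 1.0 point; 6.25 × 0.40 = 2.5 points.
- k = 8: 2.5 × 0.25 = 0.6 points; 6.25 × 0.25 = 1.6 points.

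Without GMMH the difference in this case is zero. If leniency is the same at every site, the difference is 2.5 (or 6.25) points with or without GMMH. Leaving GMMH out therefore tests the ownership conflict and nothing else.

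**4. How easily the indicator is met.** Let X and Y be the numbers rejected by the tool and usual routes, with n referrals each (n assumed): X ~ Bin(n, r(1 − L)) and Y ~ Bin(n, r), independent and without clustering. The exact probability that X < Y, with r = 25% and no true effect, is:

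| L | n = 60 | n = 120 | n = 300 | n = 600 |
|---|---|---|---|---|
| 0 | 0.46 | 0.47 | 0.48 | 0.49 |
| 10% | 0.59 | 0.65 | 0.75 | 0.84 |
| 20% | 0.71 | 0.80 | 0.92 | 0.98 |

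Without leniency, chance alone meets the indicator nearly half the time. With leniency the probability rises as the data accumulate, so more referrals make the false conclusion more likely.

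**The case against.** **It is a feasibility study.** The protocol disclaims outcome measures and hypothesis testing, and the indicator is one of several in section 8.2. That is a reason to report the rates descriptively. It does not justify a directional rule that labels any favourable difference as success.

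**By-Trust tables belong in the SAP.** This stands. Their absence from the protocol is not itself a fault, and collecting data from each site leaves them possible. The fault is the stated rule in 8.2, which takes a bare reduction as sufficient.

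**Chance does most of the damage.** The table shows that the missing margin or interval is a weakness even without leniency. This also stands. An interval would deal with chance, but it would not remove bias.

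**Stronger readings that a reader might infer, and that the documents do not support:**
- *The staff who developed the content also decide on its referrals.* The protocol does not say so. Its example of content is links to other sources of help, and the provider workshops draw on staff such as clinical IT and research.
- *The bias is known to favour the tool.* It is not. Section 1 describes providers as overwhelmed, so each lenient acceptance adds to their load, and fuller forms could expose ineligibility.
- *GMMH staff gain personally.* Section 8.1 states who holds copyright, and no royalty or personal interest.
- *The protocol plans open decisions.* It is silent on masking. That route is visible is an inference, though a fair one, since the tool runs beside paper referral (section 2) and is embedded through site IT teams (section 7.1.2).

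**Conclusion.** The point holds in a limited form and is worth acting on. Accepted/rejected status is the only outcome collected for both routes, the receiving sites decide it without described masking, and section 8.2 accepts any reduction as success. Leniency alone could meet that rule: by 2.5 to 6.25 points if general, or about 0.6 to 2.5 points if confined to two of five to eight equal sites. These sizes assume 25% usual rejection and leniency of 1 in 10 to 1 in 4; they illustrate what is possible and estimate nothing. The GMMH localities are only provisional.

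A reader might also take accept/reject to be the settled outcome for research question 6. It is not: section 4.2 counts alternative support as success too, and the concern applies only where unsuccessful means rejected by CAMHS. Nor would a result that survives the removal of GMMH be free of bias, because professionals at every provider contribute content.

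**What to change.** 1. **Definition.** Give successful and unsuccessful one meaning that can be measured on both routes, and use it in sections 1, 4.1, 4.2 and 8.2.
2. **Section 4.2.** Compare the routes within Trust, report the rates by Trust, and repeat the comparison without the GMMH sites. State that this repeat checks the ownership conflict only.
3. **Section 8.2.** Replace the achieved reduction with the estimated difference between routes and an interval that allows for clustering by referrer and site. Describe it as based on unmasked, non-randomised site decisions, and do not claim a reduction that rests on GMMH sites alone.
4. **Limitation.** State that bias shared by all sites remains and that these analyses cannot reveal it.

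A data field for whether the deciding team took part in WP2 is worth adding only if some deciding teams took no part; otherwise it has no comparison group.

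The cost is a few tables and some redrafting. Per-Trust numbers will be small, the interval will probably be wide, and the claim will be less favourable than the present wording allows.
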